##### 7.1.6.1. Summaries of AE incidence in Combined Severity Grade Subsets

For TEAEs described below, summaries will be provided by SOC, PT, treatment group, and study phase:

- All TE treatment-related AEs
- All TE SAEs
- All TEAEs leading to premature discontinuation of study drug
- TEAEs of interest:
  - injection site reactions (based on Gilead medical search terms provided by DSPH)

A brief, high-level summary of AEs described above will also be provided by treatment group and study phase.

In addition to the above summary tables, all TEAEs will be summarized by PT only, in descending order of total frequency. Summaries of all TEAEs by SOC, PT, and maximum severity will also be provided.

Multiple events will be counted only once per subject in each summary. Adverse events will be summarized and listed first in alphabetic order of SOC and PT in descending order of total frequency within each SOC. For summaries by severity grade, the most severe grade will be used for those AEs that occurred more than once in an individual subject during the study.

In addition, data listings will be provided for the following:

- All AEs, indicating whether the event is treatment-emergent
- SAEs
- Deaths
- AEs leading to premature discontinuation of study drug

## **7.2.           Laboratory Evaluations**

A by-subject listing for laboratory test results will be provided by subject ID number and visit in chronological order for hematology and serum chemistry separately. Values falling outside of the relevant reference range and/or having a severity grade of 1 or higher on the common terminology criteria for adverse events (CTCAE) severity grade will be flagged in the data listings, as appropriate.

No formal statistical testing is planned.

### **7.2.1.       Summaries of Numeric Laboratory Results**

In the case of multiple values in an analysis window, data will be selected for analysis as described in Section 3.8.3.

Descriptive statistics for laboratory tests will not be presented.

### **7.2.2.       Graded Laboratory Value**

The CTCAE Version 4.03 will be used to assign toxicity grades (0 to 5) to laboratory results for analysis. Grade 0 includes all values that do not meet the criteria for an abnormality of at least Grade 1. For laboratory tests with criteria for both increased and decreased levels, analyses for each direction (ie, increased, decreased) will be presented separately.

#### **7.2.2.1. Treatment-Emergent Laboratory Abnormalities**

Treatment-emergent laboratory abnormalities are defined as values that increase at least 1 toxicity grade from baseline at any postbaseline time point, up to and including the date of last dose of any study drug plus 30 days for subjects who permanently discontinued study drug.

If the relevant baseline laboratory value is missing, any abnormality of at least Grade 1 observed within the time frame specified above will be considered treatment emergent.

#### **7.2.2.2. Summaries of Laboratory Abnormalities**

The summaries (number and percentage of subjects) for treatment-emergent laboratory abnormalities will be provided by lab test, treatment group and treatment period; subjects will be categorized according to the most severe postbaseline abnormality grade for a given lab test. If subject does not continue into the OLE then all treatment-emergent laboratory abnormalities will be reported in the DB treatment period (Day 1 to Week 12) summary. For subjects who continue into the OLE, treatment-emergent laboratory abnormalities during the DB treatment period are the laboratory abnormalities that started prior to the first dose of OL treatment. The laboratory abnormalities with the onset date on or after the first dose of the OL treatment and no later than 30 days after permanent discontinuation of study drug will be reported in the OLE summary.

A by-subject listing of treatment-emergent Grade 3 or higher laboratory abnormalities will be provided by subject ID number and visit in chronological order. This listing will include all test results that were collected throughout the study for the lab test of interest, with all applicable severity grades displayed.

#### **7.2.3. Liver-related Laboratory Evaluations**

Liver-related laboratory evaluations will be summarized as part of chemistry results.

#### **7.3. Body Weight and Vital Signs**

Body weight and vital signs will not be summarized or listed.

#### **7.4. Prior and Concomitant Medications**

Prior and concomitant medications will not be summarized or listed.

#### **7.5. Electrocardiogram Results**

Electrocardiogram (ECG) data will not be summarized or listed.

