No deaths, serious adverse events (SAEs), AEs that caused study drug discontinuation, or pregnancies were reported in this study. All AEs were Grade 1 or Grade 2 in severity. The most frequently reported AEs among subjects randomized to GS-5745 (ie, reported for $\geq 10\%$ of subjects in the GS-5745 group) were hypertension (2 of 15 subjects, 13.3%) and nasopharyngitis (2 of 15 subjects, 13.3%). Overall, no AE/SAE safety signals were noted during the study. All graded laboratory abnormalities were Grade 1 or Grade 2 in severity. One subject (6.7%) randomized to GS-5745 had a Grade 2 chemistry abnormality, and 2 subjects (13.3%) randomized to GS-5745 had Grade 2 hematology abnormalities. No clinically important changes from Baseline in vital signs or ECG results occurred during the study. Overall, these data indicate GS-5745 was well tolerated during the study and that GS-5745 may be beneficial in subjects with RA.

Though the sample size of the Phase 1 RA study is small and the study duration brief, results indicate GS-5745 may have clinical activity in RA. It is not yet known if the magnitude of the clinical response is sufficiently high that GS-5745 could be differentiated as a single agent for RA. However, combining GS-5745 with a TNF- α inhibitor has the potential to augment the clinic benefit of either agent alone. Therapeutic strategies that employ combinations of conventional and biologic disease-modifying antirheumatic drugs have demonstrated superior clinical responses compared to single agent approaches. Combining 2 biologics is an extension of this treatment strategy and offers an approach to achieving the treat-to-target approach to RA management specified in the ACR/EULAR treatment guidelines. Given the lack of significant immunosuppression seen with GS-5745, clinical benefit may be obtained in subjects with RA when combining this agent with a biologic DMARD, as GS-5745 is postulated to decrease RA disease activity via novel pathways which are unique or at least partially unique from those inhibited by anti-TNF or methotrexate (MTX).

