6.2. Pretreatment Assessments

6.2.1. Screening Visit (Day -35 to Day 1)

Written informed consent must be obtained from each subject before initiation of any visit procedures. After a subject has provided informed consent, the investigator will determine if the subject is eligible for participation in the study. Subjects will be screened within 35 days before randomization to determine eligibility for participation in the study. The assessment will include a review of the Inclusion/Exclusion criteria and completion of all Screening Visit procedures as outlined in [Appendix 2](#).

Subjects who do not meet the eligibility criteria will be excluded from randomization and may be considered for rescreening one time for the study in consultation with the Sponsor or its designee

Screening Assessments will include confirmation of RA diagnosis; medical /surgical history; vital signs (VS) to include blood pressure, pulse, respirations, temperature, and weight; height; complete physical exam (CPE); 12 lead ECG; and central laboratory tests including Rheumatoid Factor, anti-CCP, hematology, urinalysis, urine drug screen, chemistry panel, serum β -HCG (women of childbearing potential), QuantiFERON –Gold (QFT), HIV Serology, Hepatitis B and C serologies (if positive reflex testing for positive HBV DNA and HCV RNA), CRP, Estimated Glomerular Filtration Rate (based on MDRD study equation), TSH and HbA1c and flow cytometry for subjects who have been on rituximab. Also included are 66 swollen and 68 tender joint count assessment, Patient's and Physician's Global Health Assessment, and Patient's Assessment of Pain.

A chest x-ray if one has not been performed within 90 days of Screening and films or report available for investigator review

RA disease activity will be determined by DAS28(CRP) at Screening for inclusion criteria and for randomization stratification purposes on Day 1.

Subjects meeting all of the inclusion criteria and none of the exclusion criteria will return to the clinic within 35 days after start of screening for randomization into the study.

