6.3. Blinded Treatment Assessments (Week 1 through Week 12)

All visit tests and procedures should be completed as indicated in [Appendix 2](#). Joint counts, patient global assessment of pain, physician's assessment of global disease activity, patient's

assessment of physical function, SF-36, HAD-QI should be administered prior to lab draws and study drug administration, as much as possible.

On-Treatment Assessments

- Concomitant medications
- Vital signs
- CPE at Week 12 and at ESDD if not done in the prior 12 weeks
- Targeted Physical exam (TPE) at all other visits
- 12 lead ECG at Week 12 and ESDD if not done in the prior 12 weeks
- hsCRP
- ESR
- urinalysis
- Clinical laboratory tests: hematology, chemistry panel on Study Day 1, Weeks 1, 4, 12, and at the 30-day safety follow-up (if applicable)
- Serum β -HCG (Week 12 and 30-day follow-up and ESDD), and urine pregnancy tests on Day 1 and every 4 weeks in women of childbearing potential.
- Subject questionnaires and disease activity measures will be administered at Day 1, Weeks 1, 4, 8 and 12, ESDD and 30-day follow-up (if applicable)
- Subjects with positive HBV Core Ab and/or HCV Ab during Screening should have the respective DNA or RNA PCR test for viral load every 3 months during the study; a positive test for hepatitis virus should lead to study discontinuation as per Section 3.5.2.
- Estimated glomerular filtration rate (eGFR) based on MDRD at week 12, 30 day follow-up and ESDD (calculated at central lab)

Pharmacokinetics/pharmacodynamics:

PK blood draws: PK blood draws will be done prior to dosing at Weeks 1, 4 and 8, anytime on Week 12 and at ESDD (if applicable)

Optional PK Sub-study: PPD

GS-5745 Anti-Drug Antibodies (ADA): Blood draws for ADAs will be done prior to dosing on Study Day 1, Weeks 4 and 8, anytime at Week 12 and the 30-day follow-up visit of the blinded period.

Biomarker Blood Draws: Blood biomarkers will be collected at Day 1, Weeks 4 and 12 in the blinded period of the study. In the OLE biomarker samples will be collected every 3 months starting at week 24.

Genomic Testing

Optional Genomic Testing: **PPD**

Description of Selected Assessments

Physical Exam

A CPE is required at Screening, Week 12 of the blinded period, and Week 64 of the OLE. A TPE will be performed at other study visits. A limited physical exam is defined as an examination driven by subject signs/symptoms and/or adverse events. Height is captured at screening only.

Vital Signs

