7.4. Gilead Reporting Requirements

Depending on relevant local legislation or regulations, including the applicable US FDA Code of Federal Regulations, the EU Clinical Trials Directive (2001/20/EC) and relevant updates, and other country-specific legislation or regulations, Gilead may be required to expedite to worldwide regulatory agencies reports of SAEs, serious adverse drug reactions (SADRs), or suspected unexpected serious adverse reactions (SUSARs). In accordance with the EU Clinical Trials Directive (2001/20/EC), Gilead or a specified designee will notify worldwide regulatory agencies and the relevant IEC in concerned Member States of applicable SUSARs as outlined in current regulations.

Assessment of expectedness for SAEs will be determined by Gilead using reference safety information specified in the investigator's brochure.

Any SAEs that are attributed to background RA medication (subject's TNF inhibitor or MTX) by the investigator will be forwarded to the relevant marketing authorization holder.

All investigators will receive a safety letter notifying them of relevant SUSAR reports associated with any study IMP. The investigator should notify the IRB or IEC of SUSAR reports as soon as is practical, where this is required by local regulatory agencies, and in accordance with the local institutional policy.

7.5. Clinical Laboratory Abnormalities and Other Abnormal Assessments as Adverse Events or Serious Adverse Events

Laboratory abnormalities are usually not recorded as AEs or SAEs. However, laboratory abnormalities (eg, clinical chemistry, hematology, urinalysis) independent of the underlying medical condition that require medical or surgical intervention or lead to investigational

medicinal product interruption or discontinuation must be recorded as an AE, as well as an SAE, if applicable. In addition, laboratory or other abnormal assessments (eg, electrocardiogram, X-rays, vital signs) that are associated with signs and/or symptoms must be recorded as an AE or SAE if they meet the definition of an AE (or SAE) as described in Sections 7.1.1 and 7.1.2. If the laboratory abnormality is part of a syndrome, record the syndrome or diagnosis (ie, anemia) not the laboratory result (ie, decreased hemoglobin).

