8.6. Safety Analysis

All safety analyses will be performed using the safety analysis set.

Safety will be evaluated by assessment of clinical laboratory tests, physical examinations, vital signs measurements at various time points during the study, and by the documentation of AEs.

All safety data collected on or after the first dose of study drug administration up to 30 days after the last dose of study drug will be summarized by treatment group according to the study drug received.

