Appendix 10. Frederica's Formula and Estimated Glomerular Filtration 12-Lead ECG

Subjects will be required to rest in a supine position for \geq 5 minutes prior to making a recording.

The investigator (or qualified designee) should review the ECG traces recorded in real time for clinically significant abnormalities. On treatment ECGs should be compared to the subject's Baseline as part of routine safety monitoring. The Frederica Formula will be calculated by the sponsor.

Fredericia Formula (QTcF)

$$QTc = QT/(RR^{0.33})$$

<http://www.thecalculator.co/health/QTc-Calculator-385.html>

Estimated Glomerular Filtration

Modification of Diet in Renal Disease (MDRD) formula.- Standardized Formula

$$175 \times \text{serum Creatinine (mg/dl)} - 1.154 \times \text{Age} - 0.203 \times 1.212 \text{ (if Black)} \times 0.742 \text{ (if Female)}$$

The eGFR will be calculated by the sponsor.

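### SAP 7.5 gives ECG data neither a summary nor a listing, so an asymptomatic ECG or QTcF change not reported as an adverse event reaches no planned output

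*SAP*

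**What the plan says.** **Collection.** A 12-lead ECG is part of Screening (Protocol 6.2.1). In the blinded period Protocol 6.3 asks for "12 lead ECG at Week 12 and ESDD if not done in the prior 12 weeks", and the Appendix 2 schedule carries the same condition in a footnote. In the open-label extension (OLE) the only scheduled ECG is at Week 64 (Protocol 6.4). Appendix 2 also allows one at an unscheduled OLE visit, at the investigator's discretion.

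**Purpose.** Protocol Appendix 10 has the investigator review tracings in real time for clinically significant abnormalities and compare on-treatment tracings with Baseline as safety monitoring. On QTcF it says: "The Frederica Formula will be calculated by the sponsor".

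**Planned reporting in the protocol.** Protocol 8.6 says that "All safety data collected on or after the first dose of study drug administration", up to 30 days after the last dose, will be summarised by treatment group.

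**Route into adverse events.** Protocol 7.5 sets this rule: "laboratory or other abnormal assessments (eg, electrocardiogram, X-rays, vital signs) that are associated with signs and/or symptoms must be recorded". The entry is an adverse event, serious or not, provided that the finding satisfies the protocol's definition of one.

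**Planned reporting in the SAP.** SAP 7.5 says "Electrocardiogram (ECG) data will not be summarized or listed". SAP 7.7 attributes the limited safety summaries to the low number of subjects enrolled before termination. SAP 1 says that the document supports a synoptic report, and SAP 1.3 gives enrolment as 15.

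**The concern.** Safety and tolerability as an add-on to a TNF inhibitor and methotrexate is a secondary objective (Protocol 2, SAP 1.1). ECGs were scheduled to serve it, but none of their values is due to appear in the report. The usual back-up is adverse event reporting, and here that route is obligatory only for a symptomatic abnormality. QTcF is the weakest link. The site reads the tracing, the sponsor calculates QTcF, and nothing in the documents says that the value goes back to the site for assessment as a possible adverse event.

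At stake is a plain sentence in the report. For the Phase 1 study in rheumatoid arthritis, with 15 subjects on GS-5745 and 3 on placebo, Protocol 1.3.1 could say: "No clinically important changes from Baseline in vital signs or ECG results occurred during the study". From its planned outputs, the present study could neither make nor refute that statement on ECGs.

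**Working it through.** The plan gives no ECG figure to reproduce. The check is a reading of the texts together with a count of tracings.

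**1. Does any planned output carry an ECG value?** SAP 7.5 rules out both a table and a listing, and no other SAP section provides for ECG measurements. The number of ECG or QTcF values reported is therefore zero.

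**2. What could bring an ECG finding into the report indirectly?**
- *Symptomatic abnormality that meets the AE definition:* must be recorded (Protocol 7.5), so it appears in the AE tables and listing (SAP 7.1.6.1).
- *Asymptomatic abnormality that the investigator chooses to report:* may be recorded, because Protocol 7.1.1 counts any unfavourable sign and the Grade 1 wording in Appendix 4 includes asymptomatic diagnostic observations. It then appears in the same outputs.
- *Change that leads to stopping study drug:* can appear in the discontinuation outputs (SAP 4.1, 7.1.6.1).
- *Asymptomatic change, including a QTcF change, not reported as an AE:* appears nowhere.

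Only the last case is lost.

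**3. Does the stated reason cover the omission?** SAP 7.7 speaks of limited summaries. With few subjects, summary statistics say little and a listing is the natural substitute. The SAP makes that substitution twice: it drops laboratory descriptive statistics (7.2.1) but lists laboratory results by subject (7.2), and it drops the adherence summary but lists study drug administration (4.2.2). It does not do so everywhere, since vital signs (7.3) and concomitant medications (7.4) also get neither.

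**4. How many tracings?** Inputs: 15 subjects enrolled (SAP 1.3), with one Screening ECG and one at Week 12 or ESDD per subject.
- Blinded-period total: 15 × 2 = 30 at most.
- Screening tracings, all pre-dose: 15 × 1 = 15.
- Post-dose tracings: 30 − 15 = 15 at most.

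The post-dose number may be lower, because an ESDD ECG is required only if none was done in the prior 12 weeks (84 days). The Screening window is 35 days. A subject screened the full 35 days before Day 1 needs no ESDD ECG when stopping within 84 − 35 = 49 days of Day 1. For one screened just before Day 1, that period extends to about 84 days, which is the whole blinded period. An early stopper may therefore have no post-dose tracing at all.

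**5. How long would a listing be?** Two to three tracings per subject give 15 × 2 = 30 to 15 × 3 = 45 rows. The upper figure supposes that every subject also had a Week 64 or unscheduled ECG. The documents do not say whether anyone reached Week 64.

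**The case against.** The strongest case is that this is a deliberate and disclosed reduction. The sponsor terminated the study after 15 subjects. The SAP says that some planned analyses will not be done, and section 7.7 is headed as a change from the protocol's safety analyses. Protocol 8.6 names laboratory tests, physical examinations, vital signs and adverse events as the safety evaluations, and does not name ECG. Sections 8.6.1 to 8.6.3 plan no ECG analysis, so no specified ECG output was removed. Vital signs, which Protocol 8.6 does name, are dropped as well.

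Most of this stands. It makes the omission a reporting gap and not an error, and it leaves only the general all-safety-data sentence of Protocol 8.6 as a protocol basis. It does not explain why a listing was dropped along with the summary.

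A reader might infer three stronger things that the documents do not support:
- *That any asymptomatic on-drug ECG change disappears.* Protocol 7.5 sets a minimum for recording and does not bar the investigator from reporting more. Whatever is reported appears in the AE outputs.
- *That about 30 on-drug tracings go unreported.* Half of that maximum are Screening tracings, taken before dosing.
- *That urinalysis is lost in the same way,* because the by-subject laboratory listing in SAP 7.2 is "for hematology and serum chemistry separately". SAP 7.2.2.2 summarises treatment-emergent graded abnormalities by laboratory test and lists those of Grade 3 or higher, without restricting either to those two panels. A loss of urinalysis data is not established.

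**Conclusion.** The point holds in a limited form and is minor. Under SAP 7.5, an asymptomatic ECG or QTcF change that is not reported as an adverse event would appear in no planned table or listing, although the ECGs were scheduled for safety monitoring. Low enrolment justifies leaving out summaries but not a by-subject listing.

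The size is at most about 15 scheduled post-dose tracings in the blinded period. This assumes that all 15 enrolled subjects were dosed and had one such tracing each. No rate of ECG change can be derived from the documents, so nothing can be said about whether a finding was in fact missed. No efficacy result and no specified safety analysis is affected.

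**What to change.** Replace the text of SAP 7.5 with wording such as:

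> A by-subject listing of all ECGs collected (Screening, Week 12, ESDD, unscheduled and any Week 64) will be provided by treatment group. It will show QT, QTcF and the change in QTcF from the pre-dose ECG and, where captured on the eCRF, heart rate and the investigator's interpretation.

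The condition on the last two items is needed because the eCRF is not among the documents. The listing fits the convention already set in SAP 3, where by-subject listings cover the All Randomized Analysis Set and are sorted by treatment group. No summary table or test is needed.

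The cost is a little programming and a few pages in the synoptic report, about 30 to 45 rows, with no new data collection. It would let the report state what the ECGs showed.

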#### **7.6. Other Safety Measures**

A data listing will be provided for subjects who become pregnant during the study.

#### **7.7. Changes From Protocol-Specified Safety Analyses**

Only limited safety summaries are provided due to low number of subjects enrolled in the study prior to the study termination.

## **8. PHARMACOKINETIC ANALYSES**

No PK analysis will be conducted due to the study early termination.

## **9. BIOMARKER ANALYSIS**

No biomarker analysis will be conducted due to the study early termination.

